| Blood chemistry, LFTs, LDH, amylase, lipase, hematology, coagulation g | X e     | X  | X      | X h | X h      | X h | X g,h | X g,h | X                                | X                               |
| TSH and FT4   | X e,h,i |    |        |                | X i      |                | X i   |                  | X                                |                                 |
| PSA j  | X e,h   |    |        |                | X h      |                | X h   |                  | X                                |                                 |
| PAP   | X e,h   |    |        |                | X h      |                | X h   |                  | X                                |                                 |
| Blood for PBMC immunophenotyping k                                     | X                  |    |        | X              | X                   |                | X                |                  | X                                |                                 |
| Blood for cytokine analysis l  | X                  |    |        | X              | X                   |                | X                |                  | X                                |                                 |
| Tumor biopsy m   |                    |    |        |                | X m      |                |                  |                  | X m                   |                                 |
| SRF617 administration n  | X                  |    |        | X              | X                   | X              | X                | X                |                                  |                                 |

|   | Cycle 1       |    |        |         | Cycle 2 and Cycle 3   |         | ≥ Cycle 4     |         | End of Treatment a | Safety Follow-up b |  |  |
|---|---------------|----|--------|---------|---|---------|---------------|---------|-------------------------------|-------------------------------|--|--|
|   | (28 ± 2 days) |    |        |         | (28 ± 2 days)   |         | (28 ± 2 days) |         |                               |                               |  |  |

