b All patients will have a Safety Follow-up visit approximately 30 days after the last dose of SRF617, 30 days after the last dose of etrumadenant, or 90 days (+ 7 days) after the last dose of zimberelimab (30 days after the last dose of zimberelimab if the patient initiates a new anticancer therapy), whichever is later. If possible, this visit should occur before the initiation of any subsequent anticancer therapy. At minimum, this visit should include collection of AEs/SAEs and concomitant medications/procedures. This can be performed by telephone call if the patient does not require laboratory and/or other procedures related to any new or ongoing AEs, in which case, a clinic visit will be required.

c SAEs for all patients will be reported from the time of signing the ICF through 30 days after the last dose of SRF617, 30 days after the last dose of etrumadenant, or 90 days after the last dose of zimberelimab (30 days after the last dose of zimberelimab if the patient initiates new anticancer therapy), whichever is later (Section 8.1). Nonserious AEs are collected and monitored from the time of first dose through 30 days after the last dose of SRF617, 30 days after the last dose of etrumadenant, or 90 days after the last dose of zimberelimab (30 days after the last dose of zimberelimab if the patient starts another anticancer therapy), whichever is later. Clinically significant medical conditions observed at Screening that do not meet criteria for an SAE should be recorded as part of the patient's medical history. Pregnancies occurring in partners of male patients are considered immediately reportable events if the pregnancy occurs during the study treatment period through 30 days after the patient's last dose of SRF617, 30 days after the last dose of etrumadenant, or 90 days after the last dose of zimberelimab, whichever is later.

d Physical examination will include an evaluation of disease-relevant systems and capture of vital signs. See Section 6.1.5 for more details.

e The following Screening evaluations performed within 7 days of the first dose (C1D1) can be used to meet C1D1 criteria and do not need to be repeated: physical examination, ECOG performance status, coagulation parameters, TSH, FT4, PSA, PAP, LDH, amylase, and lipase.

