f An additional blood sample for SRF617 PK and ADA should be drawn if a patient presents with a toxicity that meets the safety stopping rules, including such a toxicity outside of Cycle 1. See Section 4.6 and Section 6.1.12 for more details.

g Blood chemistry, LFTs, and hematology will be performed at every trial visit prior to dosing. On C1D2, sample collection should occur 24 ( $\pm$  2) hours post infusion of the last administered study drug. On each D1 and D15 infusion visit, sample should be collected within 48 hours before dosing of SRF617/the first infusion study drug. LDH, amylase, and lipase will be collected within 48 hours before dosing of SRF617/the first infusion study drug on D1 of each cycle. Additional (unscheduled) assessments should be performed as clinically indicated. After Cycle 5, only hematology and blood chemistry including LFTs and LDH will be performed. Coagulation parameters will be assessed only at Screening and C1D1 and then as needed. If patient is on anticoagulation that affects PT/INR or aPTT, the appropriate parameter(s) should be measured on D1 of each cycle prior to dosing. See Section 6.1.8 for detailed parameters.

h Sample collection should be completed within 48 hours before dosing of SRF617/the first infusion study drug.

i TSH and FT4 should be collected within 48 hours of D1 of every other cycle after C1D1 (eg, C3D1, C5D1, C7D1, etc). If TSH and/or FT4 result(s) are outside of the normal range, test(s) should be repeated, treatment should be initiated if appropriate, and results recorded at each visit until they are back to Baseline.

j The Investigator should follow PSA every cycle. If it is standard of care to follow a biomarker at a frequency other than once per cycle, Investigator should follow standard of care.

k PBMC samples will be collected within 24 (+2) hours before dosing of SRF617 at C1D1, C1D15, C2D1, C3D1, C4D1, C7D1, and EoT.

l Blood samples for analysis of cytokines, chemokines, and other soluble factors collected at C1D1 and C3D1 should be collected before dosing of SRF617, and 6 hours  $\pm$  15 minutes post SRF617 infusion. C1D15 and all other samples on D1 of a cycle should be collected before dosing of SRF617. EoT samples may be collected at any time during the visit.

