##### 1.4.1. Summary of Nonclinical Safety of SRF617

The nonclinical toxicology program conducted in support of clinical trials for SRF617 consisted of 2 in vivo repeated-dose intravenous (IV) injection studies in cynomolgus monkeys, an in vitro cytokine release study using human peripheral blood mononuclear cells (peripheral blood mononuclear cells [PBMCs]), and an in vitro off-target binding study using human HEK293 cells. The in vivo toxicology studies of SRF617 were conducted in cynomolgus monkeys, which was the only species identified as pharmacologically relevant based on SRF617 avidity for CD39. Both in vivo toxicology studies were conducted by the IV route of administration, which is the current clinical route of administration. The pivotal toxicology study was conducted in accordance with Good Laboratory Practice (GLP) regulations.

The weight of evidence from all the pharmacology and toxicology studies conducted with SRF617 in vitro and in vivo supports its safety in the treatment of patients with advanced cancer. All the in vivo safety studies conducted with SRF617 resulted in no significant findings up to 100 mg/kg, corresponding to an average maximum serum concentration of 4,950,000 ng/mL and area under the curve of 91,400,000 h\*ng/mL. Biologic activity of SRF617 in cynomolgus monkeys was confirmed by an in situ CD39 enzymatic activity assay.

Preclinical evidence implicates CD39 in murine models of thromboregulation. In CD39-haploinsufficient mice, there is an increase in thrombogenesis under certain vascular conditions. Although no evidence of disordered platelet activation or thrombogenesis was detected in SRF617 nonclinical studies, including nonhuman primate toxicology studies, this clinical trial will monitor for laboratory evidence of such effects, and all thromboembolic adverse events (AEs) will be recorded and monitored as adverse events of special interest (AESIs).

[figure not shown]

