11.4 Clinical Laboratory

For lab values in the form of $<x$, $\leq x$, below lower quantification limit, etc., the value will be imputed as $x/2$ or half of the lower quantification limit for the purpose of numerical descriptive summary. For lab values in the form of $>x$, $\geq x$, above upper quantification limit, etc., the value will be imputed as x or upper quantification limit for the purpose of numerical descriptive summary. When such imputation occurs, footnotes will be presented to clarify the imputation rule. The original lab values will be presented in data listings.

11.4.1 Hematology, coagulation, clinical chemistry, thyroid function tests, testosterone, PAP and PSA

The Laboratory test value, change from baseline, and percentage change from baseline for continuous parameters over hematology tests, chemistry tests, coagulation tests, thyroid function tests, testosterone, PAP and PSA will be summarized using descriptive statistics (n, mean, SD, median, minimum, maximum) by visit.

Shift of hematology tests, coagulation tests, and chemistry tests from baseline CTCAE grade to the worst postbaseline CTCAE grade will be presented. If a parameter includes both hypo- and hyper- CTCAE grade derivation, hypo- and hyper- will be tabulated separately. If the baseline is not CTCAE gradable (e.g., AST increase), the baseline measurement will be categorized as low/normal/high according to reference ranges. The programmatic grading will be modified from the CTCAE by using numerical lab results only, ignoring any other grading conditions in the CTCAE, e.g., clinical symptoms or signs.

Additionally, the liver function tests (AST, ALT, ALP, and Total Bilirubin (TBL)) will be summarized in the following categories:

- Aspartate Aminotransferase (AST)
 - >3 x ULN
 - >5 x ULN
 - >10 x ULN
 - >20 x ULN
- Alanine Aminotransferase (ALT)
 - >3 x ULN
 - >5 x ULN
 - >10 x ULN
 - >20 x ULN
- AST or ALT
 - >3 x ULN
 - >5 x ULN
 - >10 x ULN
 - >20 x ULN
- Total Bilirubin (TBL)
 - >1.5 x ULN
 - >2 x ULN
- Alkaline Phosphatase (ALP)
 - >1.5 x ULN
 - >2 x ULN
- (AST or ALT) and TBL
 - AST or ALT > 3 x ULN and TBL > 1.5 x ULN
 - AST or ALT > 3 x ULN and TBL > 2 x ULN
- (AST or ALT) and ALP and TBL
 - AST or ALT > 3 x ULN and ALP < 2 x ULN and TBL > 2 x ULN

Laboratory hematology, chemistry, coagulation, thyroid function tests will be provided in data listings by patient.

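### Under Table 2 footnote g, patients not on PT/INR- or aPTT-affecting anticoagulants have no scheduled PT/aPTT after the first SRF617 dose, so the SAP coagulation tables cannot describe SRF617's effect

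*Protocol*

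**What the plan says.** Protocol Section 1.4.1 cites mouse data linking CD39 to thromboregulation. It notes that SRF617's nonclinical studies detected no disordered platelet activation or thrombogenesis, and adds that "this clinical trial will monitor for laboratory evidence of such effects, and all thromboembolic adverse events (AEs) will be recorded" and followed as adverse events of special interest (AESIs). It names no laboratory test.

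In Table 2, the row beginning "Blood chemistry, LFTs, LDH, amylase, lipase, hematology, coagulation" is marked at every visit from C1D1 through End of Treatment and Safety Follow-up. The row label carries footnote g, which states "Coagulation parameters will be assessed only at Screening and C1D1 and then as needed". One group is treated differently: "If patient is on anticoagulation that affects PT/INR or aPTT, the appropriate parameter(s) should be measured on D1 of each cycle prior to dosing". Section 6.1.8 names PT and aPTT as the coagulation panel and likewise asks for serial monitoring only under such anticoagulation.

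On timing, footnote g says "On each D1 and D15 infusion visit, sample should be collected within 48 hours before dosing of SRF617/the first infusion study drug". Footnote e says "The following Screening evaluations performed within 7 days of the first dose (C1D1) can be used to meet C1D1 criteria", and coagulation parameters are on its list.

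SAP 5.3 takes as baseline the last available value before the first SRF617 dose. SAP 11.4.1 plans by-visit summaries of coagulation values and change from baseline, and adds "Shift of hematology tests, coagulation tests, and chemistry tests from baseline CTCAE grade to the worst postbaseline CTCAE grade will be presented".

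**The concern.** Three parts of the plan do not fit together. The background section makes a commitment, the schedule grid appears to honour it, and the footnote withdraws the coagulation part of it for patients not on relevant anticoagulants. The SAP then builds tables as though post-dose coagulation values would be available generally.

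At stake is how those tables would be read. Thromboembolic events are the trial's only AESI, so a coagulation shift table invites a conclusion about SRF617. If the post-baseline values come from patients whose PT or aPTT is altered by another drug, or who were tested because something had happened, the table shows anticoagulation and selection. A small number of abnormal shifts could also be taken as reassurance when few patients were tested. The primary efficacy endpoint is unaffected.

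**Working it through.** The plan states no figure on this point, so there is none to reproduce. The check is a count of scheduled samples, followed by a sensitivity range.

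**1. Scheduled post-dose samples.**
- Table 2 row read without the footnote, Cycles 1 to 3: C1 D2, D8, D15 (3), plus C2 D1, D15 and C3 D1, D15 (4), giving 3 + 4 = 7. Day 1 and Day 15 of each later cycle, End of Treatment and Safety Follow-up come on top.
- Under footnote g, no relevant anticoagulant: Screening and C1D1 only. C1D1 is drawn before dosing or replaced by a Screening value from the preceding 7 days. Both precede SRF617, so both are baseline under SAP 5.3. Scheduled post-baseline values: 0.
- Under footnote g, on a relevant anticoagulant: one per cycle from C2D1.

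**2. How many patients could supply a scheduled post-dose value.** SAP Section 2 gives 15 treated patients. The documents do not give the share on relevant anticoagulants, *a*, or the share of the others tested as needed, *u*. Both are assumptions here.
- Expected number with a scheduled post-dose value: 15 × *a*.
- Probability that at least 8 of 15 have none: binomial tail with success probability 1 − *a*.
- Anticoagulated patients form the majority of those with any post-dose value only if 15*a* > 15(1 − *a*)*u*, that is, *u* < *a*/(1 − *a*).

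| *a* | 15 × *a* | P(majority have no scheduled value) | *u* must stay below |
|---|---|---|---|
| 10% | 1.5 | 1.00 | 11% |
| 20% | 3.0 | 0.996 | 25% |
| 30% | 4.5 | 0.95 | 43% |
| 40% | 6.0 | 0.79 | 67% |
| 50% | 7.5 | 0.50 | 100% |

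**3. What thin data do to detection.** Suppose 10% of patients truly had a post-dose coagulation abnormality (assumed). The chance of seeing at least one is 1 − 0.9^15 = 79% if all 15 are tested, but 1 − 0.9^3 = 27% if only 3 are.

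**4. Whose values they are.** Inclusion criterion 14 exempts anticoagulated patients from the 1.5 × ULN limit on PT/INR and aPTT, provided they are in therapeutic range. Exclusion criterion 18 admits patients with prior deep vein thrombosis on stable anticoagulation. Their results carry the effect of another drug.

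**5. How the SAP would display this.** SAP 4.2 sets percentage denominators to the whole analysis set by default and shows missing counts, but not by anticoagulant use. SAP 4.3 rules out subgroup analyses.

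**The case against.** The strongest reply is that the schedule is a deliberate and ordinary choice. The Table 2 row bundles several tests, and narrowing a bundled row is what footnotes are for. Footnote g also restricts LDH, amylase and lipase to Day 1 although the row is marked on other days, and Section 6.1.8 agrees with it on coagulation. That stands: the difference between grid and footnote is not by itself an error, and how often to run PT/aPTT is for the sponsor to decide.

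It is also fair that Section 1.4.1 names no test, and that monitoring is not absent. Hematology, including platelet count, is done at every trial visit and continues after Cycle 5. Unscheduled tests are allowed when clinically indicated. Thromboembolic events, serious or not, are reported by the SAE route and tabulated. A reader might infer that the commitment is simply not met. The documents do not support that: it is met in part, and the gap is specific to PT/aPTT.

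A reader might also infer that most patients will have no on-treatment coagulation value, or that the shift table will consist mainly of anticoagulated patients. Neither follows from the documents. They give neither share, and the second statement already fails if 10% are anticoagulated and more than 11% of the others are tested as needed.

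Finally, SAP 4.2 already shows numbers with data and numbers missing, and the coagulation and concomitant-medication listings would let a reader identify anticoagulant users by hand. That reduces the problem without removing it, because the summary tables would still mix untested patients with values of two different origins.

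**Conclusion.** The point holds in a limited form. For a patient not on an anticoagulant affecting PT/INR or aPTT, footnote g leaves zero scheduled coagulation values after the first SRF617 dose. That result comes from the text alone. It fits poorly with the Table 2 row and leaves the Section 1.4.1 laboratory commitment met on schedule only through platelet counts.

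The SAP 11.4.1 coagulation tables would then rest on anticoagulated patients and clinically prompted tests, in unknown proportions, and could not support a statement on SRF617's effect on coagulation. This assumes that sites follow the footnote rather than the grid, and that unscheduled results count towards the worst grade, which SAP 11.4.1 does not say. The patient numbers and detection probabilities are illustrations under assumed shares.

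The consequence is one safety output that cannot be interpreted as planned. It is worth correcting but does not threaten the trial's main conclusions.

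**What to change.** - **Protocol.** Reconcile the Table 2 row, footnote g and Section 1.4.1 so that the stated commitment matches what is collected. Which of them changes is the sponsor's decision. Enrollment had stopped with 15 patients treated, so a schedule change now would recover little data; the SAP change matters more.
- **SAP 11.4.1.** Report the number of patients with a post-baseline coagulation value. Use patients with both a baseline and a post-baseline value as the denominator for the shift table. Present change and shift separately for patients on and not on anticoagulants affecting PT/INR or aPTT. Write the split in as an explicit exception to SAP 4.3.

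The cost is minor programming. With 15 treated patients the cells will be small, so the split will serve to show where the values come from and will not support a comparison of the groups.

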## **4. TRIAL DESIGN**

This is a Phase 2, open-label, safety and preliminary efficacy trial in patients with mCRPC who have progressed on or after prior ARSI therapy. The trial will enroll approximately 40 patients. A patient is enrolled in the trial after they have provided informed consent and met all trial eligibility criteria.

The trial will employ a Simon 2-stage design with an integrated safety lead-in for the triplet combination of SRF617, etrumadenant, and zimberelimab. Cycles are 28 days in duration.

Tumor biopsies are optional; they will be performed to explore potential biomarkers of response to the combination in patients who consent to the procedure, who have non-bone metastases amenable to biopsy, and for whom the procedure is deemed safe.

Patients will continue to receive study drug for up to 2 years or until documented disease progression or unacceptable toxicity (Section 4.7). Patients may remain on study drug longer than 2 years with agreement from the trial Investigator and Sponsor.

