### **6.3.1. Response Evaluation Criteria**

PCWG3 criteria will be applied at the time points specified in the Schedules of Assessments ([Table 2](#)). Assessment of response will be evaluated by computed tomography or magnetic resonance imaging of chest/abdomen/pelvis and bone scan every 12 weeks. PSA assessment will be performed every cycle. Patients should continue past PSA progression until clear radiologic progression or clinical progression (eg, symptomatic or physical deterioration in the absence of

radiographic progression that meets PCWG3 criteria). If osseous disease is present at Baseline, disease assessment will follow the 2+2 rule to discriminate between flare and true progressive disease in bone lesions. The Screening bone scan will be used as the Baseline scan. Patients will be permitted to continue on study drug past progression if the Investigator feels the patient is otherwise experiencing clinical benefit and Sponsor agrees (see Section 6.3). However, if a repeat scan 4 to 8 weeks after initial progressive disease confirms additional progression per PCWG3 criteria, the patient should discontinue study drug(s).

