## 9.5. Efficacy Analyses

ORR will be assessed separately by PCWG3 criteria as well as RECIST v1.1. The primary response endpoint is defined as the proportion of patients achieving PSA50 and/or radiographic objective response of CR/PR measured using PCWG3 criteria. PSA response (PSA50) is defined as a confirmed PSA decrease from Baseline of 50% or more based on 2 consecutive assessments measured 3 to 4 weeks apart. Changes in PSA across the trial period will be described using a waterfall plot. Swimmer plots will be used to describe time on trial, including timing and incidence of treatment past progression and timing of SAEs or AESIs, and may be used to reflect the concept of no longer clinically benefiting.

For efficacy endpoints derived from progression and/or response status, disease assessments after the start of new anticancer therapy will be excluded from consideration.

The number and percentage of patients with best overall response per PCWG3 criteria and per RECIST v1.1 in each of the response categories will be presented. ORR will be estimated by the percentage of patients achieving a best overall response of CR or PR. The estimated ORR along with the 2-sided 80% and 95% exact CIs will be provided.

Time-to-event endpoints such as the following will be summarized and estimated via the Kaplan-Meier method if the number of events is adequate:

- DoR, defined as the time from the first documented response (PSA50 and/or CR/PR) to documented disease progression as determined by applicable disease criteria, or documented death due to any cause, whichever occurs first. PSA50 and objective responses (CR or PR) will also be assessed individually.
- DCR, defined as the percentage of patients with CR, PR, or stable disease lasting a minimum of 12 weeks
- PFS, defined as the time from the first treatment on trial with study drug to documented disease progression as determined by applicable disease criteria or death
- Landmark PFS, defined as the percentage of patients who have not developed PFS events (ie, death or documented disease progression as determined by applicable disease criteria) at 6 months, 12 months, 18 months, and 24 months
- Time to PSA progression
- Time to radiologic progression

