3.4 Response-Evaluable Analysis Set

The Response-Evaluable Analysis Set is defined as all enrolled patients who received SRF617 and had at least 1 post-Baseline response assessment (including PSA assessment and/or tumor assessment) or who discontinued the treatment phase because of radiographic or symptomatic disease progression (including death caused by disease progression) within 6 weeks (+ 2-week window) of the first dose of SRF617. This analysis set will be the primary analysis set for the primary efficacy endpoint and other efficacy endpoints.

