10.1.2 PSA₅₀ Response

PSA₅₀ response (PSA₅₀) is defined as a confirmed PSA decrease from Baseline of 50% or more based on 2 consecutive assessments measured 3 to 4 weeks apart. PSA₅₀ response rate is the proportion of patients with PSA₅₀.

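### Table 2 footnote j lets PSA sampling follow local practice, so on schedules of 6 weeks or longer a PSA50 response cannot be confirmed without an extra draw

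*Protocol*

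**What the plan says.** **Schedule.** Protocol section 6.3.1 states "PSA assessment will be performed every cycle". The synopsis (Response Assessments) and SAP section 10 say the same, with no exception. In protocol Table 2 the PSA row is marked on Day 1 of each cycle and at end of treatment. Protocol section 4 gives the cycle length: "Cycles are 28 days in duration". Table 2 allows 28 ± 2 days, and its footnote h sets the sampling window: "Sample collection should be completed within 48 hours before dosing of SRF617/the first infusion study drug".

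**Exception.** Footnote j, attached to the PSA row, opens with "The Investigator should follow PSA every cycle" and continues "If it is standard of care to follow a biomarker at a frequency other than once per cycle, Investigator should follow standard of care". It gives no shortest or longest interval and does not mention confirmation.

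**Endpoint.** Protocol section 9.5 defines PSA50 as a "confirmed PSA decrease from Baseline of 50% or more based on 2 consecutive assessments measured 3 to 4 weeks apart", and SAP section 10.1.2 uses the same rule. PSA50 and/or a confirmed CR/PR makes up the primary composite (SAP 10.1.3). Two PSA50 responses, or one CR/PR, among 17 evaluable patients allow Stage 2 to be considered (protocol 9.1).

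**Denominator.** Under SAP section 3.4 an enrolled patient who received SRF617 is response-evaluable if he "had at least 1 post-Baseline response assessment (including PSA assessment and/or tumor assessment"). SAP section 5.4.2 says that missing data are in general not imputed. SAP section 10.1.2 has no rule for PSA pairs that fall outside 3 to 4 weeks.

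**The concern.** The per-cycle schedule is what supplies the pair of values that PSA50 needs. Footnote j tells the Investigator to leave that schedule where local practice differs, so whether a decline can be confirmed may depend on habit at about 15 sites in two countries. A patient whose PSA falls by 50% and stays down, but who is sampled at long intervals, has no qualifying pair and counts as having no PSA50 response. One post-Baseline PSA is enough to place him in the denominator, so at the long intervals the error runs one way, toward a lower response rate. Patients with non-measurable disease are eligible (inclusion criterion 7), and for them PSA may be the main practical route to a response. The composite rate is also the only efficacy result that SAP version 2.0 keeps.

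**Working it through.** **1. The design's own figures.** Inputs from protocol 9.1: 17 + 23 = 40 patients, success at 8 or more responses, null 10%, alternative 30%. The Stage 1 rule is taken as at least 2 responses of 17. Formula: P(pass) = Σ over x ≥ 2 of P(X₁ = x | 17, p) × P(X₂ ≥ 8 − x | 23, p). At p = 0.10 this gives 0.0399, and at p = 0.30 it gives 0.934. The stated alpha of 0.040 and power of 0.93 are reproduced.

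**2. Which sampling intervals can satisfy the rule.** Confirmation must be "based on 2 consecutive assessments measured 3 to 4 weeks apart", read literally as 21 to 28 days.

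| PSA every | Gap between consecutive draws | Within 21–28 days? |
|---|---|---|
| 1 week | 7 days | Not as adjacent draws; pairs 21 and 28 days apart exist |
| 2 weeks | 14 days | Not as adjacent draws; pairs 28 days apart exist |
| 3 weeks | 21 days | Yes |
| 4 weeks (one cycle) | 28 days | Yes |
| 6 weeks | 42 days | No, and no other scheduled pair qualifies |
| 8 weeks | 56 days | No, and no other scheduled pair qualifies |
| 12 weeks | 84 days | No, and no other scheduled pair qualifies |

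The clear failure is at 6 weeks or longer. Weekly and 2-weekly sampling fail only if an intermediate draw is held to break a consecutive pair, which the SAP does not settle.

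**3. Illustrative effect on the planned design.** The documents give neither f, the share of patients on a non-qualifying schedule with no confirmatory draw, nor s, the share of responders who qualify through PSA alone. Both are assumptions here. With a true composite rate of 30%, the observable rate is 0.30 × (1 − f × s), put into the formula of step 1.

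| f | s = 1: rate | s = 1: power | s = 0.5: rate | s = 0.5: power |
|---|---|---|---|---|
| 0 | 0.300 | 0.934 | 0.300 | 0.934 |
| 10% | 0.270 | 0.869 | 0.285 | 0.906 |
| 20% | 0.240 | 0.761 | 0.270 | 0.869 |
| 30% | 0.210 | 0.606 | 0.255 | 0.820 |

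The Stage 1 gate moves less. P(at least 2 of 17) is 0.98 at a rate of 0.30 and 0.97, 0.94 and 0.90 at 0.27, 0.24 and 0.21.

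**4. The analysis that will now be done.** SAP sections 1.1 and 2 report termination with 15 patients treated, and SAP 10.2.1 tests the composite rate against 10% with a one-sided exact test. If all 15 are evaluable, P(X ≥ 4 | 15, 0.10) = 0.056 and P(X ≥ 5 | 15, 0.10) = 0.013.

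**5. A related limit in the rule itself.** With a 28 ± 2 day cycle and samples allowed up to 48 hours before dosing, a compliant pair of Day 1 samples can be 29 or 30 days apart, just outside a literal 4 weeks.

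**The case against.** A reader might infer that PSA50 is out of reach for anyone not sampled once per cycle. The documents do not support that. A 3-weekly schedule meets the rule, and more frequent sampling fails only on a strict reading of consecutive. A confirmatory draw is not forbidden either: protocol section 6.1.8 lists PSA among the laboratory tests and provides for unscheduled assessments when clinically indicated. These points stand, and they confine the problem to long intervals with no extra sample.

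The footnote can also be read as permitting additional sampling, since its first sentence asks for PSA every cycle and patients attend on Day 1 for infusion and blood draws. That reading is possible. But the second sentence covers any frequency other than once per cycle and says the Investigator should follow it, so less frequent sampling is included. Nothing in the documents shows that any site sampled less often. Nor do they show that such sampling would escape being recorded as a deviation: it would depart from section 6.3.1, and the deviation plan is not available.

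The power figures with every response depending on PSA are a worst case, because a confirmed CR/PR still counts. They also describe a two-stage design that did not reach Stage 2. Both points are fair, which is why the half-PSA column and the 15-patient test are shown. Finally, much of the harm comes from the closed 3-to-4-week window, so correcting the footnote alone would be incomplete. That is right, and the fix covers both.

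**Conclusion.** The concern holds in a limited form. Footnote j contradicts the unconditional per-cycle schedule in the synopsis, protocol 6.3.1 and SAP section 10. At intervals of 6 weeks or more it leaves no scheduled pair that can confirm a PSA50 response, while the patient remains in the denominator. The resulting bias in the composite rate is downward and is confined to patients who depend on PSA and have no extra draw in the window.

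Its size cannot be determined from the documents. The illustrated power, with 10% to 30% of patients affected, is 0.87 to 0.61 if all responses rest on PSA and 0.91 to 0.82 if half do, against 0.93 as planned. These are scenarios, not estimates. In the terminated trial, with at most 15 patients in the test, a single unconfirmed decline could be the difference between p = 0.013 and p = 0.056. The point should be corrected. It does not show that any response was in fact missed.

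**What to change.** **Protocol, or any protocol that reuses this schedule.** Delete the second sentence of footnote j. State that PSA is drawn on Day 1 of every cycle for all patients, and that standard-of-care values may be recorded in addition but do not replace the Day 1 sample.

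**SAP section 10.1.2.** Base confirmation on the scheduled Day 1 values, so that intermediate draws do not break a pair. Apply the protocol visit window, so that a compliant pair from a 28 ± 2 day cycle qualifies.

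**Data already collected.** Report how many patients with a PSA decline of 50% or more had no qualifying confirmatory pair, next to the composite response rate.

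**Cost.** One sentence in the protocol, a short addition to the SAP and one count in the report. Patients already attend and give blood on Day 1 of each cycle, so sampling adds at most one local PSA test per cycle where it was not being done. Treatment is not changed.
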